	9.3	CONFIDENTIALITY	
	9.4	INDEMNITY	
	9.5	Sponsor	
	9.6	Funding	
	9.7	Audits	
10		UDY MANAGEMENT	
11	L PUE	BLICATION POLICY	16
12	2 REF	FERENCES	17

CSP: Conduction system pacing CT: Computed tomography ECG: Electrocardiogram

EGG. Electrocardiogram
EGM: Electrogram
HBP: His-bundle pacing
ICE: Intracardiac echocardiogram
LBBB: Left bundle branch block LBP: Left bundle pacing
LBAP: Left bundle area pacing
LV: Left ventricle
LVAT: Left ventricular activation time

MRI: Magnetic resonance imaging

RV: Right ventricle

TOE: Transoesophageal echocardiogram TTE: Transthoracic echocardiogram

Study Summary

TITLE	Fluoroless Conduction System Implant		
DESIGN	Cohort observational study and interventional at validation phase		
AIMS	Define a feasible fluoroless protocol for conduction system lead implantation		
	Primary Outcomes:		
OUTCOME MEASURES	1. Success rate of conduction system lead implant Secondary Outcomes: 2. Fluoroscopy time 3. Total procedure time 4. Capture threshold 5. Number of times leads deployed 6. Complication rates: a. Lead implanted at the incorrect position: non-septal positions b. Lead displacement c. Lead injury d. Rise in threshold (late complication) e. Vascular injury f. Perforation with or without subsequent tamponade g. Device related infection h. Pneumothorax		

POPULATION	Patients with any indication for a pacemaker
ELIGIBILITY	Main Inclusion Criteria 1. Patients with a ventricular pacing indication: high grade atrioventricular block and symptomatic trifasicular or bifasicular block. (in order to assess the level of conduction system block) 2. Adults willing to take part (ages 18 – 100 years old) 3. Able to give consent.
	Main Exclusion Criteria 1. Unable to give consent 2. Children age < 18 years and adults > 100 years old 3. Pregnant patients 4. Pacing device in situ 5. Indication for cardiac resynchronisation therapy 5.
DURATION	1 year

1. Introduction

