1.2 Original Hypothesis

- Conduction system leads can be implanted with almost no fluoroscopy using electroanatomical mapping
- 2. Using electro-anatomical mapping will increase safety of conduction system lead implantation
- The procedure times with electro-anatomical mapping will be less than that of conventional methods using fluoroscopy

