1.3 Rational for Current Study

Currently conductions system pacing can have long fluoroscopy times when compared to conventional right ventricular pacing. This may be due to difficult cardiac anatomy, altered lead trajectory and obstacles such as entanglement, that is not readily visualised with fluoroscopy. As a result operators experience additional cumulative fluoroscopy times. Our study will devise a standardised implantation protocol using 3D electroanatomical mapping systems to reduce both fluoroscopy and procedure times.

2. Study Objectives

Primary Objective

The primary objective of this study is develop a fluoroless implant protocol of conduction system leads using 3D electroanatomical mapping.

Secondary Objective

The secondary objectives will be

- To reduce the overall procedure and fluoroscopy time with utilisation of targeted lead deployment.
- 2. Improve complication rates

3. Recruitment

A total of 75 patients will be recruited for the study

50 patients with a ventricular pacing indication (high grade atrioventricular block and symptomatic trifasicular or bifasicular block) for pacing will be recruited prospectively. The patients will be divided into two groups; 25 patients in the derivation cohort and 25 patients in the validation cohort. The derivation cohort will undergo a detailed research protocol to determine the optimised work flow and this will be applied prospectively to the validation cohort.

The success rates, procedure times, complication rates and fluoroscopy times will be assessed. The 25 patients undergoing conventional methods of conduction system pacing will be recruited as a control arm to compare these outcomes.

In summary, the 75 patients will be grouped as following; 25 patients in the derivation cohort, 25 patients in the validation cohort and 25 patients in the control arm.

4. Methodology

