The CartoMerge module will be used to expedite anatomical mapping using the MRI data collected.

- 5. The mapping catheter will be removed and an intracardiac echo (ICE) catheter, will be inserted through the femoral vein.
- 6. The conduction system pacing lead will be inserted through the axillary vein. A right atrial lead will be inserted into the right ventricular apex for back up pacing in the instance the conduction system is bumped. The basal-septum, mid-septum, high-septum and anterior walls will be paced to identify electrical markers for optimal implant sites.
- 7. The lead will be visualised on the Carto maps created.
- 8. The lead will be deployed at the predetermined target site under direct visualisation using the ICE catheter. Through direct visualisation, three key determinants can be assessed:
 - 1. Lead trajectory through the septum with the goal of achieving perpendicularity
 - Lead septum interaction and whether there is evidence of entanglement preventing lead progression.
 - Relationship between the sheath and lead that can lead to or prevent failure of lead deployment.
- 9. Once the conduction lead is secured the right atrial lead will be pulled back and secured in the right atrium.
- 10. The procedure will be completed as per standard clinical implant protocol with routine clinical follow-up thereafter:

The information from echocardiography will be corroborated with the lead-septum interaction visualised on electro-anatomical maps created on CARTO.

In this cohort of patients, the conduction system lead will initially pace the His-bundle then the left bundle in order to collect data for both methods of physiological pacing. The information collected from ICE and electro-anatomical mapping will be used to develop a streamlined workflow that will map targeted areas, where challenging implant sites will be rapidly identified (such as areas of scar), reducing the number of attempted lead deployments and visualise lead-septum interaction, apposition and progression, improving safety parameters.

At the end of the procedure, the lead position will be documented with a very short, *single fluoroscopic acquisition*. This remains integral for future comparison in the instances of lead complications and in particular lead displacement.

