4.6 Study Outcome Measures

Primary Outcome Measures

1. Success rates of conduction system lead implant (fluoroless workflow vs conventional methods)

Secondary Outcome Measures

- Procedure and fluoroscopy times of the fluoroless workflow vs current conventional methods of His-bundle and Left-bundle pacing
- Procedure and fluoroscopy times of the fluoroless workflow vs conduction system implant to current right ventricular pacing
- 3. Assess capture threshold of His-bundle and Left-bundle pacing from the fluoroless workflow vs that of conventional methods of conduction system implantation
- 4. Number of times leads deployed in the fluoroless protocol vs conventional methods of conduction system implantation
- Complication rates in the fluoroless protocol vs conventional methods of conduction system implantation:

- a. Lead implanted at the incorrect position: non-septal positions
- b. Lead displacement
- c. Lead injury
- d. Rise in threshold (late complication)
- e. Vascular injury
- f. Perforation with or without subsequent tamponade
- g. Device related infection
- h. Pneumothorax

5 Participant Entry

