25 patients will provide the ability to determine the percentage of a successful implant with a precision of a SE (\pm 8%) of a success rate of approximately 80% SD of implant time = SD of total procedure time / $\sqrt{2}$ = 67 / $\sqrt{2}$ =47.37 SE = SD/ $\sqrt{\text{sample size}}$ = 47.37/ $\sqrt{2}$ 5 = 9.47

Data and all appropriate documentation will be stored for a minimum of 5 years after the completion of the study, including the follow-up period.

To assess the primary outcome of the success rates of the conduction system lead implant using the fluoroless workflow developed during our study, ECG information will be collected and capture will be determined by experts.

Fluoroscopy and procedural times will be analysed with one-way ANOVA. Success rates, capture thresholds and battery life will be analysed with t-test.

9 Regulatory issues

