9.2 Consent

Consent to enter the study must be sought from each participant only after a full explanation has been given, an information leaflet offered and time allowed for consideration. Signed participant consent should be obtained. The right of the participant to refuse to participate without giving reasons must be respected. After the participant has entered the study the clinician remains free to give alternative treatment to that specified in the protocol at any stage if he/she feels it is in the participant's best interest, but the reasons for doing so should be recorded. In these cases the participants remain within the study for the purposes of follow-up and data analysis. All participants are free to withdraw at any time from the protocol treatment without giving reasons and without prejudicing further treatment.

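### The primary success rate rests on ECG capture and sets no fluoroscopy condition, so on its own it does not measure whether the workflow is feasible without fluoroscopy

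*Protocol*

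**What the plan says.** The Study Summary gives the aim as "Define a feasible fluoroless protocol for conduction system lead implantation". Section 2 sets the primary objective in similar terms: to "develop a fluoroless implant protocol of conduction system leads using 3D electroanatomical mapping". The first hypothesis in Section 1.2 is slightly softer: "Conduction system leads can be implanted with almost no fluoroscopy using electroanatomical mapping".

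The primary outcome in Section 4.6 is "Success rates of conduction system lead implant (fluoroless workflow vs conventional methods"). Section 8 says how it will be assessed: "ECG information will be collected and capture will be determined by experts". No other success criterion is given.

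Fluoroscopy appears in three further places:

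- Section 4.1, on the derivation cohort: "At the end of the procedure, the lead position will be documented with a very short" single acquisition. Section 4.2, on the validation cohort, has no matching statement.
- Section 4.6, as a secondary outcome: "Procedure and fluoroscopy times of the fluoroless workflow vs current conventional methods of His-bundle and Left-bundle pacing".
- Section 8, where fluoroscopy times are to be compared by one-way ANOVA.

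Section 9.2 leaves the clinician free to depart from the protocol treatment and adds: "In these cases the participants remain within the study for the purposes of follow-up and data analysis".

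**The concern.** The property under study is implantation without, or almost without, fluoroscopy. The primary outcome does not contain it. An ECG shows whether the conduction system is captured. It does not show whether the operator reached the site by mapping or turned to fluoroscopy on the way.

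If a validation patient's lead cannot be placed by mapping alone, is then placed with additional fluoroscopy, and captures, the patient meets the only criterion the protocol states. No rule says whether that patient is a success, a failure, or outside the calculation. These three choices give three different rates. If the choice is left open until the data are in, it can be made with knowledge of the result.

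At stake is the headline figure. A workflow that often needed fluoroscopic help could report the same success rate as one that never did, and the primary result would not distinguish them.

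**Working it through.** **Inputs.** From Section 8: 25 patients per group, a success rate of about 80%, and a stated standard error of 8%. The number of captures that needed additional fluoroscopy is not given anywhere. It is an assumption and is varied below.

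**The plan's own figure.** SE = √(p(1−p)/n) = √(0.80 × 0.20 / 25) = 0.080. This matches the stated 8%. The sample-size arithmetic is not in question.

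**Two definitions on the same data.** Suppose 20 of 25 patients have capture, and k of those 20 needed fluoroscopy beyond the documenting acquisition.

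- Capture alone: rate = 20/25, whatever k is.
- Capture without additional fluoroscopy: rate = (20 − k)/25.

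Exact (Clopper-Pearson) 95% intervals:

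| k (assumed) | Capture alone | Capture without additional fluoroscopy |
|---|---|---|
| 0 | 80% (59% to 93%) | 20/25 = 80% (59% to 93%) |
| 3 | 80% (59% to 93%) | 17/25 = 68% (46% to 85%) |
| 4 | 80% (59% to 93%) | 16/25 = 64% (43% to 82%) |
| 5 | 80% (59% to 93%) | 15/25 = 60% (39% to 79%) |

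Each such case moves the rate by 1/25 = 4 percentage points, so two cases (8 points) equal the stated standard error. With k = 0 the definitions agree and nothing is lost.

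**Does the secondary outcome fill the gap?** Fluoroscopy time is compared between groups by ANOVA, that is, on means. A few long rescues and uniformly short use can give the same mean. No threshold turns a patient's time into a fluoroless or not-fluoroless result, and time is not linked to success patient by patient. A raised mean would be a warning, but it would not yield the feasibility rate.

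**The case against.** The strongest reply has four parts.

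1. **The protocol never says that a fluoroscopy-assisted implant is a success.** This is correct. A reader might infer that such implants are scored as successes of the workflow, but the documents do not go that far. The Section 8 sentence on the primary outcome opens by referring to implants made with the workflow, which could be read as excluding conversions. Section 9.2 is general consent wording: keeping a patient in the analysis does not say how that patient is scored. What remains is that the classification is not stated, and that the literal criterion, capture, is met.

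2. **Feasibility can be judged from success and fluoroscopy time together.** This has some force, since both are measured in the same patients. The further inference that the trial cannot show feasibility at all is therefore too strong. But the two outcomes are planned as separate group summaries, and no planned result combines them per patient.

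3. **The comparison with controls needs a definition both arms can meet.** Agreed. A fluoroscopy-free criterion makes no sense for conventional implants, and capture success should stay for that comparison.

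4. **A strict no-fluoroscopy rule goes beyond the trial's own hypothesis, and the detail belongs in an analysis plan.** The first half is fair: the hypothesis allows a little fluoroscopy, and the single acquisition is described for derivation only. A prespecified limit would answer this. On the second half, operational detail may well sit in an analysis plan that is not shown. But the protocol itself fixes the primary outcome and its criterion, and as fixed they leave out the feature named in the aim.

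**Conclusion.** The point holds in a limited form. The aim is a fluoroless protocol, the only stated success criterion is expert-judged ECG capture, and implants completed with additional fluoroscopy are not classified. The primary rate alone therefore does not measure fluoroless feasibility, and the secondary comparison of mean fluoroscopy time only partly makes up for this.

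The possible size is 4 percentage points per converted patient: 80% against 68% if 3 of 20 captures needed additional fluoroscopy. The conversion counts are illustrative, because the protocol gives no conversion rate. The 80% is the plan's precision assumption, not a predicted validation result. If no patient needs additional fluoroscopy, the reported rate is unaffected.

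**What to change.** Keep capture success, regardless of fluoroscopy and as assigned, for the comparison with the control arm.

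In Sections 4.6 and 8, add a per-patient feasibility endpoint for the validation cohort: expert-confirmed capture with no fluoroscopy beyond the final documenting acquisition. Alternatively, use a limit on fluoroscopy that gives the Section 1.2 hypothesis a number, provided it is fixed before validation starts. State in Section 4.2 whether the documenting acquisition also applies to this cohort. Keep all 25 patients in the denominator, count any other fluoroscopy use as not fluoroless, and report the number of conversions. This is a rule for scoring only and places no restriction on the operator.

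The cost is small. The change is to endpoint wording, and fluoroscopy time is already an outcome; what needs adding to the record is whether any use went beyond the documenting acquisition. The downside is that the reported workflow success may be less favourable.

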4.1 Derivation

The derivation cohort will comprise of 25 prospectively recruited patients. These patients will undergo the research protocol. In these patients, we will attempt to implant a permanent conduction system pacing lead, in lieu of the RV or LV lead. The lead will be implanted by operators who have implanted more than 40 leads to overcome the learning curve.

Pre-implant

Prior to the procedure, patients will undergo a clinically indicated Cardiac MRI. We will use these scans to retrospectively assess for the presence of potential mechanisms which could prevent successful lead implantation, such as the presence of septal fibrosis and chamber dimensions, so that we can assess how these can contribute to challenges at the time of implant. We will also be able to review mechanisms for *successful* implants. This information will be corroborated with data collected from the electro-anatomical maps.

The MRI scans will also be used to merge the anatomical information using CartoMerge to reduce procedure times by building the anatomical geometry prior to the mapping-catheter collecting this information invasively.

During Implant

The participants will undergo the following procedural steps after written informed consent is gained:

- A left infraclavicular incision and axillary access for the lead will be gain as per standard clinical protocol.
- 2. Access from the femoral vein will be sought where a sheath will be placed in the femoral vein to introduce the mapping catheter.
- 3. Fast anatomical mapping (FAM) of the right atrial and right ventricular anatomy will be made where CartoMerge has not already created this anatomy. This will include the right ventricle, the tricuspid valve and the right ventricular outflow tract. Activation and voltage maps will be then be made of the His-bundle area (including the His cloud), right ventricle, right ventricular outflow tract and right ventricular septum.

This will help determine a few key aspects

- 1. Level of conduction system block and therefore guide site of lead deployment
- 2. Anatomy of the right heart and overcome challenges this may propose
- 3. Evidence of septal fibrosis and/or scar that need to be overcome
- 4. Activation pattern of the septum in conduction system block
- 4. Anatomical FAM maps, voltage maps and activation patterns will be compared against the data collected from the cardiac MRI to assess
 - 1. Accuracy of anatomy
 - 2. Fibrosis and scar patterns

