4.2 Validation

25 patients will be recruited to the validation cohort.

An optimised work flow will be derived using the information collected from the derivation cohort. Namely, the target areas for FAM and electro-anatomical maps will be determined, and the successful pattern of lead septum interaction on CARTO will be defined.

The streamlined workflow will then be applied to 25 prospective patients. The success rates, procedure time, fluoroscopy time, capture threshold, number of attempted lead deployments and complication rates will be assessed.

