4.3 Control Arm

The control arm will consist of 25 patients undergoing a conduction system pacemaker using conventional pacing methods, with the same pacing indications as the study arm.

[figure not shown]

Figure 1: Recruitment workflow

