4.5 Burden/Risk

The main burdens for the patient include:

- The extra time taken to perform the experiments and experimental procedures during their scheduled clinical procedure due to the additional diagnostic investigations. The right heart electro-anatomical mapping will add 10 minutes. The echocardiography will add an additional 5 minutes.
- 2. The extra access in the groin for the mapping catheter and ICE catheter.
- 3. Patients receiving unconventional therapy with conduction system lead implantation

Control Group C: N=25 (Standard of care) I. 12-lead ECG Before the Echocardiogram procedure 3. MRI of the heart I. 12-lead ECG During the 2. Fluoroscopy procedure (x-ray) Routine clinical ca Follow-up 6 weeks, 6 months, 1 v Deleted:

The burden will be mitigated by the minimum extra time being used to complete the experiments, the use of local anaesthetic and the immediate removal of extra research related sheaths as soon as they are not needed

The main risks for the patient are:

A conduction system pacing wire is not known to have a higher complication rate compared to a conventional pacing wire. Conduction system pacing wires have been shown to be as effective as conventional pacing wires at preventing slow heart rates and improving heart pumping. If a complication occurs and the conduction system pacing wire cannot be implanted or does not perform as expected during follow-up a procedure will be performed to convert your pacing system to a conventional pacing system.

The additional risks of vascular tube placement include:

- 1% risk of bruising around the area
- 1 in 1000 risk of damage to the blood vessels requiring surgery
- Less than 1 in 500 risk of stroke

The additional risks of intracardiac echocardiogram include

- 1% risk of bruising around the access area in the leg
- Less than 1 in 1000 risk of heart perforation

The additional risks of electro-anatomical mapping include

Less than 1 in 1000 risk of heart perforation

Therefore, the overall risk of serious complications arising from taking part in the research study are less than 4 in 1000 (0.4%)

Pacemaker implantation involves exposure to ionising radiation to visualise lead implantation. Taking part in this study involves exposure to additional exposure to radiation above the standard clinical procedure due to the additional measurements that will be taken.

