6.4 Serious AEs

An SAE form should be completed and faxed to the Chief Investigator within 24 hours. However, hospitalisations for elective treatment of a pre-existing condition do not need reporting as SAEs.

All SAEs should be reported to the "name of REC when allocated" where in the opinion of the Chief Investigator, the event was:

• 'related', ie resulted from the administration of any of the research procedures; and

• 'unexpected', ie an event that is not listed in the protocol as an expected occurrence

Reports of related and unexpected SAEs should be submitted within 15 days of the Chief Investigator becoming aware of the event, using the NRES SAE form for non-IMP studies. The Chief Investigator must also notify the Sponsor of all related and unexpected SAEs.

Local investigators should report any SAEs as required by their Local Research Ethics Committee, Sponsor and/or Research & Development Office.

Contact details for reporting SAEs

[contact]

[name] email: [contact]
Please send SAE forms to: [name].
[contact] (Mon to Fri 09.00 – 17.00)

7 Assessment and Follow-up

Patients will be followed up for a 1 year period. During this time they will undergo the device interrogation and wound check at 6 weeks as part of standard clinical care. One year after device implantation, patients will undergo a device interrogation follow-up appointment. Any incidental findings that we identify during the study will be reviewed by the research team and reported to the GP and also the cardiology team normally looking after the patient.

Definition of end of Study

The end of the study will be defined as completion of the 1 year follow-up of the 75 prospectively recruited patients for the invasive aspect of the study. This will be the date of the final visit of the last participant at 1 year.

8 Statistics and data analysis

The following statistical analysis has been reviewed and approved by our statistician, [name].

Power Calculations:

25 patients would provide the ability to determine the mean time of lead implantation of 120 minutes with a precision of (as a standard error) approximately \pm 10 minutes (assuming standard deviation of 47 min)⁷

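### Secondary outcome 2 compares times with right ventricular pacing, but none of the 75 patients is assigned to it and no outside series is named

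*Protocol*

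**What the plan says.** Section 4.6 gives two separate outcomes on procedure and fluoroscopy times. The first sets the fluoroless workflow against conventional His-bundle and left-bundle pacing. The second reads "Procedure and fluoroscopy times of the fluoroless workflow vs conduction system implant to current right ventricular pacing". The primary outcome and the remaining secondary outcomes (capture threshold, number of deployments, complications) are all compared with conventional methods, which for the secondary outcomes are expressly those of conduction system implantation.

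Section 3 accounts for everyone recruited: "the 75 patients will be grouped as following; 25 patients in the derivation cohort, 25 patients in the validation cohort and 25 patients", where the last 25 are the controls. It describes the controls in these words: "The 25 patients undergoing conventional methods of conduction system pacing will be recruited as a control arm to compare these outcomes".

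Sections 4.1 to 4.3 say what each group receives:

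- Derivation: "we will attempt to implant a permanent conduction system pacing lead, in lieu of the RV or LV lead".
- Validation: "The streamlined workflow will then be applied to 25 prospective patients".
- Control: "The control arm will consist of 25 patients undergoing a conduction system pacemaker using conventional pacing methods".

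The Study Summary lists fluoroscopy time and total procedure time as secondary outcomes and mentions no right ventricular comparator. Section 1.3 remarks that conduction system pacing can take longer under fluoroscopy than conventional right ventricular pacing, but gives no figure, citation or data set for this.

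**The concern.** A comparison needs data on both sides. The control arm already serves the first time outcome, so the second needs a different comparator, and the Protocol does not say where it would come from. This is not a detail that a statistical analysis plan would normally supply. An analysis plan chooses the method, but the Protocol decides who is recruited and which outcomes are promised.

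Two results are possible if the line stays. Either the outcome is listed and never reported, or someone finds a right ventricular series once the fluoroless times are known. In the second case the choice of series could settle how favourable the comparison looks. The wording adds to the difficulty: it places one comparator after *vs* and another after *to*. An analyst could not tell whether the workflow, conventional conduction system implantation, or both are to be compared with right ventricular pacing.

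**Working it through.** **The plan's own figures.** Section 8 justifies 25 patients by the precision of a single group.

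- SD of implant time = 67/√2 = 47.38 min, and SE = 47.38/√25 = 9.48 min (the Protocol gives 9.47).
- SE of an 80% success rate = √(0.80 × 0.20/25) = 0.08, which is the stated 8%.

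Both reproduce, apart from the last digit. Neither involves a comparator, so the sample size statement neither uses nor implies right ventricular data.

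**Count by type of pacing.**

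| Group | n | Pacing assigned | Source |
|---|---|---|---|
| Derivation | 25 | Conduction system | Sections 3, 4.1 |
| Validation | 25 | Conduction system, streamlined workflow | Sections 3, 4.2 |
| Control | 25 | Conduction system, conventional methods | Sections 3, 4.3 |
| Sum | 75 | | |

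Total recruited = 75. Assigned to right ventricular pacing = 75 − (25 + 25 + 25) = 0.

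**Places where a comparator might be hidden.**

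1. *The standard-of-care label on the control group*, in the figure fragment within Section 4.5. It does not mention right ventricular pacing, and Sections 3 and 4.3 say that controls have conduction system pacing.
2. *The lead at the right ventricular apex* in Section 4.1. This is a right atrial lead used for back-up during the implant and then withdrawn to the atrium. It is not a right ventricular implant with times of its own.
3. *Patients who are converted.* Section 4.5 says that if the lead cannot be implanted or performs poorly, "a procedure will be performed to convert your pacing system to a conventional pacing system". These patients would be selected by failure, and their times would include the failed attempt or belong to a second procedure. They cannot represent routine right ventricular pacing.
4. *The rationale in Section 1.3.* It makes a qualitative remark and offers no benchmark.
5. *The one-way ANOVA for times* in Section 8. It names no groups and no right ventricular source.

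None of the five supplies the missing side.

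**The case against.** The best defence is that the outcome refers to current practice, which can be read as a benchmark rather than a recruited arm. An external series would then make the comparison possible, and an analysis plan that is not shown here might name one. Part of this stands. A reader might infer that the outcome can never be produced, and the Protocol does not support that. What it supports is narrower: the outcome has no comparator within the design, and the document that lists it names no source outside the design.

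A reader might also infer from Section 7 that a retrospective right ventricular group is ruled out, since the end of study is defined by "completion of the 1 year follow-up of the 75 prospectively recruited patients". That sentence goes on to limit itself to the invasive part of the study, so it does not by itself exclude such a group. The point rests on no such group being named anywhere.

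It is also fair to say that the stakes are modest. The Study Summary omits this comparison, the first time outcome already covers the comparison the design was built for, and the tangled wording suggests a drafting slip. This limits the importance of the point, but the line remains in the list of outcomes.

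**Conclusion.** The point holds in this form: 0 of 75 patients supply the comparator for secondary outcome 2, no external or historical series is named, and the intended contrast is unclear. It rests on the text of Sections 3 and 4.1 to 4.3 and needs no numerical assumption. Figure 1 is not available, but the text places all 75 patients, and the surviving fragment of the figure shows no right ventricular group.

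The defect should be corrected but is confined to one secondary outcome. It gives no reason to doubt the primary outcome or the other secondary outcomes. If an external series is used, a reader might infer that a formal test should be avoided because 25 patients give too wide an interval. That is not the ground. Description is appropriate because the series would be non-concurrent and not comparable by design with the validation cohort.

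**What to change.** Choose one of two changes to Section 4.6.

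1. Delete secondary outcome 2. This brings the list into line with the Study Summary and removes nothing that the design can deliver.
2. Replace it with: *Procedure and fluoroscopy times in the validation cohort will be described alongside those of a named external right-ventricular-pacing series, without a formal test.* Name the series before the data are analysed, and check that its pacing indications and definitions of procedure and fluoroscopy time match those of the study.

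Either change alters one line and needs no further patients. Deletion needs no further data. The second option costs the work of finding one suitable source and specifying it in advance.
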